Esophageal food impaction is a relatively common illness, estimated to occur at a rate of 13 episodes per 100,000 people per year, mostly men, and usually attributed to swallowed meat bolus. Current standard of care for patients presenting to an Emergency Department with presumed esophageal food impaction includes trial of medical therapy, usually glucagon but sometimes effervescent liquid, sublingual or intravenous nitroglycerin, or benzodiazepines, with a backup of endoscopy for definitive mechanical removal of the food bolus. Glucagon has significant uncomfortable side effects, chiefly nausea and vomiting. The medical interventions mentioned above have not been shown to have significant efficacy; endoscopy is frequently performed after failure of medical management. There is significant risk associated with endoscopy, including the risks of anesthesia as well as with the physical procedure itself. Endoscopy also results in a prolonged hospital stay due to the time required for the procedure, as well as from anesthesia recovery. The ideal treatment would be a safe, inexpensive, quickly effective medical intervention without significant side effects that could be administered without sedation or extensive monitoring. Oral nitroglycerin solution might just be that intervention.

No published trials or case reports using oral nitroglycerin solution for esophageal food impaction were found. Two recent unpublished cases using oral nitroglycerin solution were remarkably and rapidly effective (within 2 minutes) in relieving esophageal food impaction symptoms. The currently proposed study would provide preliminary data which may motivate a larger controlled study.

4. Approach

a. Study design

Prospective, unblinded, single-arm cohort of patients presenting to the Emergency Department with presentation consistent with esophageal food impaction.

b. Population

i. Inclusion/Exclusion Criteria [See Human Subjects items to be moved here]

1. Inclusion Criteria:

- a. Over the age of 18 years
- b. Presentation consistent with esophageal food impaction
- c. Ability to swallow a small volume of liquid.

2. Exclusion Criteria:

- a. Intractable vomiting
- b. Hemodynamic instability or SBP <100 mmHg
- c. Concern for or evidence of significant airway compromise
- d. Concern for or evidence of esophageal perforation,
- e. Concern for or evidence of coronary ischemia
- f. Presentation > 12 hours since onset.

ii. Sample size

1. Convenience sample of 20 patients.

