4. A single follow-up phone call will be made by investigators and/or research assistants between 4-7 days after discharge to obtain:
 - a. Symptoms at discharge
 - b. Symptoms currently
 - c. Any other treatment required since hospital discharge
 - d. Satisfaction survey

d. *Intervention, treatments*

- i. Up to 3 administrations of 0.4mg sublingual nitroglycerin tablets, dissolved in 10mL tap water, given orally in a single swallow. Each administration is separated by at least 5 minutes, and only if systolic blood pressure > 100 mmHg. The patients then have to pass a swallow test before discharge. The passing of the swallow test will indicate a treatment success. Treatment failure is

defined as lack of symptom resolution 10 minutes after the last dose of nitroglycerin OR inability to tolerate administration OR intolerable side effects.

e. Outcomes/endpoint and other variable definitions, and instruments used

- i. Primary Endpoint is the patient is able to swallow without difficulty within 10 minutes after nitroglycerin administration.
- ii. Secondary endpoint is adverse events during the hospital stay.

f. Statistical analysis plan

- i. Descriptive statistics will be used to summarize the study sample and to evaluate efficacy of the study intervention and frequency of side effects. Specifically, we will first calculate summary statistics (mean \pm standard deviation, frequency counts and percentages) for relevant patient factors (demographics, etc.) at the time of presentation to the ED. We will then calculate the proportion of study patients who achieve resolution of food impaction, with a corresponding 95% confidence interval. Similarly, we will also report frequencies of adverse events, overall and by type of adverse event, along with appropriate measures of variance (including headache frequency and change in blood pressure). Finally we will report outcome statistics (frequency counts and percentages) for repeat symptoms subsequent to the hospital visit (from follow up phone call). Symptom data from follow-up phone call will be used, non-statistically, to identify possible delayed complications of oral nitroglycerin use.

g. Power analysis or statement of precision

- i. No formal hypothesis testing will be pursued, thus we have not conducted a power analysis.. Given the proposed sample size ($n=20$), and projecting 90% success in resolving food impaction (18/20), we anticipate a 95% confidence interval of (68.3%, 98.8%).

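### Sections 4.d, 4.e and 4.f give counting rules for efficacy that do not agree, so the one Aim 1 proportion has no single defined numerator

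*Combined protocol and SAP*

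**What the plan says.** The efficacy outcome is described in three adjacent sections of the combined protocol and SAP.

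- **4.d, success.** "The patients then have to pass a swallow test before discharge. The passing of the swallow test will indicate a treatment success." The only time limit is discharge.
- **4.d, failure.** Failure is "defined as lack of symptom resolution 10 minutes after the last dose of nitroglycerin", or not tolerating the administration, or side effects the patient cannot tolerate. Any one is enough.
- **4.d, dosing.** Up to three administrations are allowed. "Each administration is separated by at least 5 minutes."
- **4.e.** "Primary Endpoint is the patient is able to swallow without difficulty within 10 minutes after nitroglycerin administration." It does not say which administration.
- **4.f.** The plan will "calculate the proportion of study patients who achieve resolution of food impaction, with a corresponding 95% confidence interval". It gives no time limit and cites neither 4.d nor 4.e.
- **4.g.** The precision statement projects 18 of 20 successes, with a 95% interval of 68.3% to 98.8%.

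Section 3 describes the care around the study drug: medical therapy "with a backup of endoscopy for definitive mechanical removal of the food bolus", and "endoscopy is frequently performed after failure of medical management". Section 4.c.v.3 abstracts the drugs and procedures of the visit after discharge. No section says how they enter the efficacy proportion.

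**The concern.** Aim 1 is the success rate of oral nitroglycerin. The study has one arm and no hypothesis test, so this proportion is the whole efficacy result. A descriptive proportion still needs one definition of who is in the numerator, and here a patient can satisfy a stated success rule and a stated failure rule together, with nothing to say which prevails.

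The situation is foreseeable. Section 3 expects endoscopy after failed medical treatment, and a patient whose impaction has been removed may well pass a swallow test before going home. Section 4.h discloses the small sample and the missing comparison group, but not that more than one counting rule is in play. If the choice is made after the 20 records are seen, it can follow the result.

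**Working it through.** **1. Reproduce the plan's figure.** Inputs from 4.g: x = 18, n = 20, 95% confidence. The exact (Clopper-Pearson) limits are beta quantiles:

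- lower = Beta(0.025; x, n − x + 1) = Beta(0.025; 18, 3) = 68.3%
- upper = Beta(0.975; x + 1, n − x) = Beta(0.975; 19, 2) = 98.8%

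This matches 4.g. Wald (76.9 to 100) and Wilson (69.9 to 97.2) do not. The interval arithmetic is sound; the question is only what counts as a success.

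**2. Apply each rule, as written, to four kinds of patient.**

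| Patient | 4.d success sentence | 4.d failure rule | 4.e endpoint | 4.f wording |
|---|---|---|---|---|
| A. Swallows within 10 minutes of a single dose, tolerates it, passes the test | success | not a failure | met | counted |
| B. Unresolved 10 minutes after the last dose, cleared later by endoscopy or another drug, then passes the test | success | failure | not met | counted |
| C. Swallows within 10 minutes, passes the test, intolerable side effects | success | failure | met | counted |
| D. Not swallowing 10 minutes after dose 1, swallows within 10 minutes of dose 3, passes the test | success | not a failure | depends on which dose | counted |

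The rules agree on A only. B is the conflict between timed and undated rules, C the conflict over tolerability, and D the unstated clock.

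**3. The clock.** Doses are at least 5 minutes apart (4.d).

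- Third dose: 5 + 5 = 10 minutes after the first, or later.
- A 10-minute window counted from the first dose ends at 10 minutes.
- A 10-minute window counted from the last of three doses ends at 10 + 10 = 20 minutes, or later.

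A first-dose window can therefore close before the third dose has had any time to act.

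**4. Size.** One patient in 20 is 1/20 = 5 percentage points. Suppose a broader rule counts the projected 18 and a stricter rule removes k of them. The estimate becomes (18 − k)/20, with exact limits as in step 1:

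| k | Estimate | Exact 95% CI |
|---|---|---|
| 0 | 18/20 = 90% | 68.3 to 98.8 |
| 1 | 17/20 = 85% | 62.1 to 96.8 |
| 2 | 16/20 = 80% | 56.3 to 94.3 |

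The lower limit falls by 68.3 − 62.1 = 6.2 points for one patient and 68.3 − 56.3 = 12.0 points for two. The values of k are assumptions, because the documents give no rate of rescue, late resolution or intolerance.

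**The case against.** The strongest reply is that the timed rule is plainly meant. Section 4.e calls the 10-minute swallow the primary endpoint, and the 4.d failure rule already makes patient B a failure. Section 4.g uses wording close to 4.f yet projects 90%, an odd figure for planners who were counting patients cleared by endoscopy. The swallow test can be read as a check before discharge, limited by the failure definition in the same paragraph. The Data Collection Form, which is not among the documents, may define the outcome further. Most of this stands, and it makes the timed reading the likely one. It does not remove the conflict: the success sentence in 4.d still has no time limit, 4.f still points nowhere, and patients C and D remain open even under a timed reading.

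A reader might infer more: that rescue will be credited to nitroglycerin, so that the reported rate drifts to 20/20 = 100% (83.2, 100) whatever the drug does, 30 or 50 points above a timed 14/20 or 10/20. The documents do not support that. It needs a high 10-minute failure rate, clearance of every failure before discharge, and an analyst who counts defined failures as successes. None of these is given.

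A reader might also infer that the plan has no rule at all for other impaction treatment. That is too broad, since rescue after a 10-minute failure is covered by 4.d. What is not covered is another drug given before or during the window, or endoscopy in the same visit after a timed success. Section 3 says "Current standard of care for patients presenting to an Emergency Department with presumed esophageal food impaction includes trial of medical therapy, usually glucagon", so the first can happen, but the window is short and few such patients are likely. How to count them is a choice between acceptable options, and disclosure is enough.

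**Conclusion.** The concern holds as an inconsistency of definition. Sections 4.d, 4.e and 4.f must be reconciled, because followed literally they class the same patient in opposite ways in the only Aim 1 estimate. The size is 5 points per reclassified patient. One or two patients, an assumed number, would take the projected 90% to 85% or 80%. The documents do not show that any given number will be affected, or that the sponsor intends to count rescued patients as successes. The change should be made because it costs little and the sample is small. It does not affect the correctness of the interval in 4.g or the descriptive nature of the study.

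**What to change.** Before data are seen, state in 4.f, and align 4.d and 4.e with it:

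1. The analysed proportion is the timed 4.e endpoint, with all enrolled patients in the denominator.
2. There is one clock, consistent with the 4.d failure rule: 10 minutes after the last nitroglycerin dose the patient received.
3. A patient who meets any 4.d failure criterion, including those for tolerability, is a non-success.
4. A swallow test first passed after that time, or after endoscopy or another impaction drug given following a 10-minute failure, does not turn a failure into a success.

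As a descriptive check, report how many counted successes had another impaction drug or endoscopy recorded during the visit. This leaves the primary estimate unchanged and shows the reader how far it can be attributed to nitroglycerin.

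The cost is a few sentences. The check uses items already abstracted under 4.c.v.3. Those are listed without times, so it describes the whole visit rather than the window. The time at which swallowing is assessed must be recorded; whether the Data Collection Form already does so cannot be seen from the documents. The downside is that the reported success rate may be slightly lower. The change concerns analysis wording only and alters no dose, schedule or clinical decision.

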Official Title: Esophageal Food Impaction (ONEFIT)

NCT#: NCT03305848

Study Protocol and Statistical Analysis Plan

Document Date: July 26, 2017

Participant Contact Project Narrative

1. Summary

A piece of food stuck in the esophagus (the tube connecting the mouth to the stomach) is a relatively common occurrence, estimated at a rate of 13 episodes per 100,000 people per year, mostly men, and usually attributed to swallowed meat. The current standard of care for patients presenting to an Emergency Department with this problem includes a trial of medication, usually glucagon but sometimes a carbonated beverage, an injection of nitroglycerin, or benzodiazepines. The medical interventions mentioned above have not been shown to be significantly effective and have unwanted side effects; glucagon is known to cause nausea and vomiting and benzodiazepines can cause sedation and depressed breathing. If the medication fails to relieve the problem, the patient may require a procedure called endoscopy, where a video scope and retrieval tool are inserted into the esophagus to remove the piece of food. There is significant risk associated with endoscopy, including the risks of anesthesia as well as with the physical procedure itself. Endoscopy also results in a prolonged hospital stay due to the time required for the procedure, as well as from anesthesia recovery. The ideal treatment would be a safe, inexpensive, quickly effective medication without significant side effects that could be administered without sedation or extensive monitoring. Oral nitroglycerin solution might just be that intervention.

2. Study aims

Obtain exploratory data on the safety and efficacy of oral nitroglycerin solution for the treatment of esophageal food impaction in a cohort of patients presenting to the ED with presumed esophageal food impaction.

Aim 1: Efficacy. We will determine the success rate of oral nitroglycerin solution in relieving the food impaction by assessing the resolution of symptoms and the ability of the patient to swallow.

Aim 2: Safety. We will calculate the frequency of adverse events from this medical intervention. We are mainly concerned with hypotension, lightheadedness, headache, allergic reaction, dyspnea, vomiting, and pain.

3. Background, Rationale, Significance

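### No listed follow-up call item records an untreated symptom that starts after discharge and resolves before the call, so the planned repeat-symptom count is incomplete

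*Combined protocol and SAP*

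**What the plan says.** Aim 2 (Section 2) sets no time limit on safety: "We will calculate the frequency of adverse events from this medical intervention". Section 4.e.ii then sets one: "Secondary endpoint is adverse events during the hospital stay".

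The only contact after discharge is described in Section 4.c.v, item 4: "A single follow-up phone call will be made by investigators and/or research assistants between 4-7 days after discharge to obtain" four things. They are "Symptoms at discharge", "Symptoms currently", "Any other treatment required since hospital discharge" and "Satisfaction survey".

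Section 4.f relies on this call twice. It plans frequency counts and percentages of repeat symptoms after the visit, with the call as the source. It also states: "Symptom data from follow-up phone call will be used, non-statistically, to identify possible delayed complications of oral nitroglycerin use".

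Section 7.b limits medical record access to the specific admission. Section 4.c.iv refers to an attached Data Collection Form that defines the variables; the form is not reproduced in the document.

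**The concern.** Both tasks that Section 4.f gives the call concern an interval: what happened between leaving hospital and the call. The two symptom items each concern one moment, the day of discharge and the day of the call. A symptom that falls wholly between those moments is recorded only if it led to treatment.

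Several events named in Aim 2, such as headache, lightheadedness, vomiting and pain, can be brief and go untreated. A repeat impaction can also clear without care. At stake is the completeness of the repeat-symptom percentage, and of the informal look for delayed complications, in a study meant to provide preliminary data for a larger controlled one (Section 3).

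**Working it through.** **1. The plan's own figure.** Section 4.g gives a 95% interval of (68.3%, 98.8%) for 18/20 successes. The exact Clopper-Pearson limits are the 2.5% quantile of Beta(18, 3) = 68.30% and the 97.5% quantile of Beta(19, 2) = 98.77%. The figure reproduces. It is not in dispute and does not bear on the call; it only confirms n = 20 and the interval method.

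**2. Which post-discharge symptoms can be recorded.** Setting the call items (4.c.v, item 4) against the possible courses of a symptom that starts after discharge:

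| Course of symptom | Discharge item (a) | Current item (b) | Treatment item (c) | Recorded? |
|---|---|---|---|---|
| Still present at call | no | yes | if treated | yes |
| Resolved, treated | no | no | yes | yes |
| Resolved, untreated | no | no | no | no listed item |

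The satisfaction survey (item d) has no stated content, so nothing can be assumed from it.

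**3. Whether another source fills the last row.** Interviews take place at enrollment and after each administration (4.c.v, item 1), so before discharge. Chart abstraction after discharge (4.c.v, item 3) covers the visit, and 7.b restricts access to that admission. Neither source reaches the interval.

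**4. Whether item (a) is needed.** Symptoms throughout the ED visit are collected under 4.c.v, item 1, and condition at discharge under 4.c.v, item 3.e. For patients discharged from the ED, item (a) largely repeats this from memory 4-7 days later.

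**5. Size.** One patient is 1/20 = 5 percentage points, assuming all 20 are reached by telephone. The documents give no post-discharge symptom rate, so what follows is illustration only. Let p be the proportion of patients with such a symptom and t the share of those that were treated or still present at the call. Expected number missed = 20 × p × (1 − t).

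| Assumed p | Assumed t | Expected with symptom | Missed | Shortfall in percentage |
|---|---|---|---|---|
| 10% | 50% | 2 | 20 × 0.10 × 0.50 = 1.0 | 5 points |
| 10% | 25% | 2 | 20 × 0.10 × 0.75 = 1.5 | 7.5 points |
| 30% | 50% | 6 | 20 × 0.30 × 0.50 = 3.0 | 15 points |
| 30% | 25% | 6 | 20 × 0.30 × 0.75 = 4.5 | 22.5 points |

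If no repeat symptoms are reported in 20 patients, the upper 95% Clopper-Pearson limit is 1 − 0.025^(1/20) = 16.8%. That limit applies only to the kinds of symptom the call can detect, that is, the first two rows of the table in step 2.

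**The case against.** The strongest reply is that the call already does most of what is asked of it. The treatment item covers the whole interval, so a repeat impaction that needed care is counted even if resolved. The two symptom items together identify patients who were well at discharge and unwell at the call. What is lost is untreated and self-limiting, and so probably milder. This stands, and it rules out two readings that a reader might reach: that the call asks about nothing except two moments, and that it cannot deliver either of its assigned outputs. It delivers both, incompletely.

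The listed items are also topics and not a script, and the Data Collection Form may contain more. This stands as a limit on the point: it concerns the list as written in the protocol.

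Section 6.a describes the drug's half-life as very short, which is the plan's own reason to expect acute systemic effects early. That weakens the case for late direct drug effects. It does not touch repeat impaction, which Section 4.f undertakes to count.

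Finally, in a 20-patient study with no comparison group, handling post-discharge symptoms descriptively is a defensible choice. That also stands, and the fix below keeps to it.

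**Conclusion.** The point holds in a narrow form. Followed as written, the call list leaves untreated symptoms that start and resolve between discharge and the call unrecorded. The repeat-symptom percentage in Section 4.f is then incomplete and probably low, by an amount the documents do not allow to be estimated. The scale is 5 points per missed patient. The conclusion assumes that the Data Collection Form adds no further call question and that patients do not volunteer such events. In an exploratory, descriptive study it is minor.

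Three stronger inferences are not supported:

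- *The in-hospital adverse event frequency is biased low.* Section 4.e.ii defines that frequency for the hospital stay, and later events cannot bias a quantity defined for an earlier window. The fair comment is that the window is narrower than Aim 2 suggests.
- *The loss is greatest in treatment successes because they leave soonest.* Section 6.b lists avoided admission and endoscopy among the potential benefits, but the documents give no discharge times, so this remains conjecture.
- *The loss can be sized by a contrast such as 3/20 = 15% (3.2-37.9) against 5/20 = 25% (8.7-49.1).* Those counts would be assumed, and the contrast shows the effect of widening the endpoint window. A better call question alone would leave the in-hospital figure unchanged.

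**What to change.** In Section 4.c.v, item 4, replace item (a) with a question on any new or recurrent symptoms at any time since discharge, with time of onset and of resolution. Check the Data Collection Form first; if it already has such a question, list it in the protocol and the point is closed.

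In Section 4.f, state that symptoms from discharge to the call will be reported descriptively as their own window, with the number of patients reached as denominator. Do not pool them with the in-hospital adverse event frequency. Add that, without a comparison group, they cannot be attributed to the drug; a pooled total would count background headache or pain as events of the intervention.

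The cost is one reworded question on a call already planned and a line or two of SAP text, with no added visit or patient. The downsides are reliance on recall over 4-7 days, which item (a) already has, and the counting of some background symptoms.
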